3.1 Number/Source/Screening

The trial will accrue a maximum of 750 patients in 2-3 years. Patients with either ALI or ARDS will be recruited from intensive care units in approximately 24 hospitals that comprise the NIH ARDS Network.

Study coordinators at each site will visit each intensive care unit daily to identify potential candidates for enrollment (see inclusion criteria, section 3.2 and exclusion criteria, section 3.3). Permission to approach patients/families will be requested from attending physicians. Demographic and physiologic data from all patients meeting the study inclusion criteria (section 3.2) will be entered on a screening log. The

screening log will include information explaining why patients meeting the inclusion criteria are not enrolled (exclusion criteria, attending physician denial, patient refusal, etc.).

3.2 Inclusion Criteria [37]

Acute Onset of:

1. $\text{PaO}_2/\text{FiO}_2 \leq 300$. If altitude $> 1000\text{m}$, then $(\text{PaO}_2/\text{FiO}_2) (300 \times (\text{B.P.}/760))$.
2. Bilateral infiltrates consistent with pulmonary edema on frontal Chest radiograph. The infiltrates may be patchy, diffuse, homogeneous, or asymmetric.
3. Requirement for positive pressure ventilation through an endotracheal tube.
4. No clinical evidence of left atrial hypertension. If measured, pulmonary arterial wedge pressure ≤ 18 mmHg.

Criteria 1-3 must all be observed within a 24-hour interval.

“Acute onset” is defined as follows: the duration of the hypoxemia criterion (#1) and the chest radiograph criterion (#2) must be ≤ 28 days at the time of randomization.

3.3 Exclusion Criteria

1. Clinicians caring for patient refuse to use volume Assist/Control ventilation for at least 12 Hours after patient randomization. (This exclusion criterion is intended to avoid randomization of patients who may begin weaning within 12 hours. Other forms of ventilation or gas exchange support, such as pressure control ventilation or ECMO, are not allowed in this study after 12 hours).
2. Age < 13 years.

3. Participation in other intervention trials for ALI, ARDS, or sepsis within the past 30 days.
4. > 36 hours since all inclusion criteria were met (see “Enrollment Time Window”, Section 3.4).
5. Neuromuscular disease that impairs ability to ventilate spontaneously, such as C5 or higher spinal cord injury, amyotrophic lateral sclerosis, Guillain-Barre syndrome, and myasthenia gravis.
6. Pregnancy (negative pregnancy test required for women of child-bearing potential required prior to randomization).
7. Elevated intracranial pressure (Appendix A), tricyclic antidepressant overdose (if most recent blood level is elevated or no blood level available), Hgb SS, Hgb SC, or conditions in which hypercapnia would be contraindicated (attending physicians will be advised that hypercapnia may occur).
8. Severe chronic respiratory disease (e.g. COPD, pulmonary fibrosis, morbid obesity, and other chronic diseases of the lung, chest wall or neuromuscular system (Appendix A)).
9. Morbid obesity > 1 kg/cm body weight).
10. . Burns \geq 30% total body surface area.
11. Malignancy or other irreversible disease or condition for which 6-month mortality is estimated \geq 50%.
12. Bone marrow transplant.
13. Lung transplant.
14. Not committed to full support (Exception: A patient will not be excluded if he/she would receive all supportive care except for attempts at resuscitation from cardiac arrest).
15. Severe chronic liver disease [Child-Pugh Score of 10-15 [38] , Appendix A.
16. Vasculitis with diffuse alveolar hemorrhage.

3.4 Enrollment, Randomization, and Study Initiation Time Window

All patients must be enrolled, randomized, and initial ventilator adjustments made within 36 hours of the time the last inclusion criterion was met. The last inclusion criterion may be met at either the network hospital or a referring hospital. The 36-hour window for randomization will begin at the time of documentation of the last inclusion criterion, regardless of hospital location. Initial ventilator changes must occur within 4 hours of the time of randomization, and must be made within 36 hours of the time that the last inclusion criterion was met.

3.5 Informed Consent

Informed consent will be obtained from each patient or surrogate.

3.6 Randomization

After obtaining a signed and dated informed consent, the data coordinating center will be called and an assignment will be made by computer-generated randomization to either the Higher ELV/Lower FiO₂ or the Lower ELV/Higher FiO₂ study group. Randomization will be in permuted blocks by hospital.

Randomization will be accomplished with Interactive Voice Response technology. Each research coordinator will have a unique Personal Identification Number (PIN). She or he will call the system and provide the PIN. The IVR system will assign either the Higher ELV/Lower FiO₂ or Lower ELV/Higher FiO₂ ventilation strategy and a patient ID number.

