The primary efficacy measure is mortality prior to hospital discharge to day 60 after randomization. Patients alive in hospital at day 60 will be considered to have survived. This efficacy measure has been used to calculate sample size and to develop interim stopping boundaries.

Since survival ALI/ARDS patients may be affected by many other factors that are indirectly or remotely related to mortality, several secondary outcome variables will also be examined. These are chosen to reflect morbidity and cost of medical care:

1) Number of Ventilator Free Days (VFDs): the number of days after initiating unassisted breathing to day 28 after randomization, assuming a patient survives for at least 48 consecutive hours after initiating unassisted breathing. For example, if a patient initiates unassisted breathing on day 16 and survives to day 28, he/she will be assigned a value of 12 VFDs. If a similar patient begins unassisted breathing on day 16 but dies on day 25, he/she will be assigned a value of 9 VFDs. If a patient survives for > 48 consecutive hours of unassisted breathing but requires assisted breathing (for any reason) before day 28, he/she will be assigned only the number of days of unassisted breathing before day 28. Patients who die without initiating unassisted breathing or before 48 consecutive hours of unassisted breathing will be assigned a value of zero VFDs. Patients transferred to another hospital or other health care facility prior to day 28 (intermediate care, nursing home etc.) while still on positive pressure ventilation will be followed to assess this efficacy measure.

VFDs is related to the “days of assisted ventilation”, which would be a simpler measure. However, if there were a trend in one treatment group towards more rapid death on assisted ventilation, the effect of this trend on days of assisted ventilation would be misleading. “Average duration of ventilation in survivors” would avoid this potential problem. However, if there were a trend towards lower mortality in one treatment group with greater days of assisted ventilation in survivors in that group, the measure of days of assisted ventilation in survivors would be misleading. VFDs will be favorably affected by both lower mortality and shorter duration of ventilation in survivors.

- 2 Percentage of patients who achieve 48 consecutive hours of unassisted breathing at 28 days after randomization
- 3 Number of ICU-free days at 28 days after randomization.

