5.1 Background Assessments

1. Demographic and Admission Data.
2. Pertinent Medical History and Physical Examination.
3. Height; calculated predicted body weight (PBW).
4. Time on ventilator prior to enrollment.
5. Type of Admission
 - (a) Scheduled surgical
 - (b) Medical
 - (c) Unscheduled surgical
6. Presence of following chronic diseases:
 - (a) Metastatic cancer (proven by surgery, computed tomographic scan, or other documented method).
 - (b) Hematologic malignancy (lymphoma, acute leukemia, or multiple myeloma).
 - (c) AIDS with complications (PCP pneumonia, Kaposi's sarcoma, lymphoma, tuberculosis, or toxoplasmosis).

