5.4 Endpoint Determinations

1. Vital status at 28 days.
2. Time of initiation of unassisted breathing.
3. Status 48 hours after initiation of unassisted breathing.
4. Date of ICU discharge.
5. Date of hospital discharge.
6. Vital status at 60 days if still in hospital.

6 Statistical Considerations

The primary objective of this trial is to compare mortality prior to hospital discharge in ALI/ARDS patients who receive a Higher ELV/Lower FiO₂ ventilation strategy versus a Lower ELV/Higher FiO₂ strategy. The Lower ELV/Higher FiO₂ strategy is identical to the 6 ml/kg tidal volume strategy used in the recently completed ARDS Network trial. In this previous study, mortality prior to hospital discharge to 60 days after randomization in the 6 ml/kg tidal volume group was 28%. For this study, it is assumed that mortality prior to hospital discharge to day 60 in the Lower ELV/Higher FiO₂ study group will be 28%. This new study will accrue up to 750 subjects and have an 89% chance of finding a significant mortality benefit of the Higher ELV/Lower FiO₂ strategy if the true difference is 10% or greater (from 28% to 18%) using a one-sided 0.025 significance level test (equivalent to a two-sided $p = 0.05$ significance level).

The trial will be monitored by a Data and Safety Monitoring Board (DSMB). Two interim analyses are planned, after 250 and 500 subjects have completed the trial procedures. The trial may be stopped by the DSMB for futility of the Higher ELV/Lower FiO₂ strategy at the first interim analysis if mortality in the Higher ELV/Lower FiO₂ group is less than that observed in the Lower ELV/Higher FiO₂ group. The trial may be stopped at the second interim analysis if mortality in the Higher ELV/Lower FiO₂ group is not at least 2% better. At each interim analysis, overall mortality will be assessed prior to comparison of the group mortality rates. If the overall mortality is such that the futility boundary

would not maintain at least 90% power to detect an absolute 10% difference in mortality, then the futility boundary will be adjusted. If there is no true difference in mortality between study groups, there is a 50% chance that the trial will stop for futility at the first interim analysis and an additional 24% chance of stopping for futility at the second interim analysis.

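### Section 6 describes the mortality comparison on raw group rates, with no baseline covariate; prespecified adjustment would gain some power and precision at little cost

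*Supplement*

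**What the plan says.** - **Randomisation (Section 3.6).** "Randomization will be in permuted blocks by hospital". The block size is not given. Section 3.1 adds: "Patients with either ALI or ARDS will be recruited from intensive care units in approximately 24 hospitals".
- **Endpoint (Section 2).** "The primary efficacy measure is mortality prior to hospital discharge to day 60 after randomization". It is binary.
- **Baseline data.** Section 5.1 lists "Demographic and Admission Data", type of admission and chronic diseases. Section 5.2 lists blood gases, FiO₂ and PEEP, creatinine, platelets, Glasgow coma score and vasopressor use, recorded before the initial protocol ventilator changes.
- **Analysis (Section 6).** "This new study will accrue up to 750 subjects", with 89% power for 28% against 18% mortality, "using a one-sided 0.025 significance level test". The interim looks at 250 and 500 patients compare the mortality rates of the groups. The efficacy boundary is 2.0·√(3/i). The trial may stop for futility at look 1 if mortality is higher in the Higher ELV group (as corrected on the front page), and at look 2 if the benefit is below 2 points.

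Section 6 names no test statistic, no stratification factor and no covariate, and it does not rule them out. The amendments do not touch this section. No separate analysis plan is shown.

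**The concern.** Variables of the kind that often predict death in intensive care are recorded before treatment, yet the comparison as described makes no use of them. Two things are at stake.

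1. **Efficiency.** When covariates explain part of the outcome, an adjusted comparison has a smaller standard error for the same number of patients.
2. **Chance imbalance.** If one arm happens to receive sicker patients, the raw difference moves. Adjustment chosen after that has been seen is open to the charge of being post hoc. The protocol knows this threat: Section 1.2.2 gives a possible excess of high-risk controls as one reason why an earlier 53-patient trial is hard to interpret. This trial is far larger, but its futility rules act on raw differences at 250 and 500 patients, and the second threshold is only 2 points.

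**Working it through.** **Inputs from the protocol.** 375 patients per arm (half of 750), mortality 28% and 18%, one-sided 0.025, looks at 250, 500 and 750, boundaries 2.0·√(3/i) = 3.46, 2.45 and 2.00, and the two futility rules, treated as binding.

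**Assumptions, not in the protocol.** Covariate R² of 0.02 to 0.20 on the risk-difference scale, and a between-hospital SD of 0 to 0.8 on the logit scale.

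**1. Reproduce the stated power.** For a single unadjusted look:

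- √(2 × 0.23 × 0.77) = 0.595 under the null, and √(0.28 × 0.72 + 0.18 × 0.82) = 0.591 under the alternative
- z = (0.10 × √375 − 1.96 × 0.595) / 0.591 = 1.30, so power is 90.4%

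Simulating 2 million trials of the unadjusted two-proportion z test with all three looks and both futility rules gives 88.8% (pooled standard error) or 88.9% (unpooled), with one-sided type I error 0.024. Futility stops under no difference are 47% and then 26%, against the stated 50% and 24%; look 1 becomes 50% if ties are split. The 89% is therefore the power of an unadjusted test.

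**2. Power with adjustment.** Same design, with the standard error multiplied by √(1 − R²), by normal approximation. The N for equal power is 750 × (1 − R²).

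| Assumed R² | Power | Gain (points) | N for unchanged power |
|---|---|---|---|
| 0 | 88.5% | – | 750 |
| 0.02 | 89.1% | 0.6 | 735 |
| 0.05 | 89.9% | 1.4 | 712 |
| 0.10 | 91.4% | 2.9 | 675 |
| 0.15 | 92.8% | 4.3 | 638 |
| 0.20 | 94.1% | 5.6 | 600 |

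Type I error stays at 0.024 throughout.

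**3. Contribution of hospital.** Patient-level simulation at a single look: 24 hospitals, blocks of 4 (assumed), 1,500 trials per scenario, between-hospital SD 0 or 0.4.

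- A hospital-stratified Cochran-Mantel-Haenszel test changed power by less than 0.5 points from the unadjusted test in every scenario. The largest change was 91.1% to 91.5%.
- Under no difference (SD 0.4 or 0.8, 4,000 trials each), one-sided error was 0.020 to 0.024 when hospital was ignored and 0.023 to 0.026 with stratification. The Monte Carlo error is about 0.0025. Ignoring hospital is slightly conservative if anything.

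**4. Noise from chance imbalance.** At pooled mortality 23%, with n per arm, the covariate part of the raw risk difference has a 95% range of ±1.96 × √(R² × 0.23 × 0.77 × 2/n). At R² = 0.10:

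- 250 patients (n = 125): ±3.3 points
- 500 patients (n = 250): ±2.3 points
- 750 patients (n = 375): ±1.9 points

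For proportion, the whole sampling range at 500 patients is ±1.96 × √(0.1771 × 2/250) = ±7.4 points. Removing the covariate part leaves 7.4 × √0.90 = ±7.0.

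**The case against.** The strongest objection is that silence is being read as a decision. Section 6 gives a significance level within a power statement and describes the interim comparison; neither defines the final model. A sample size on raw proportions does not commit a trial to an unadjusted analysis, and covariate choice is commonly left to an analysis plan, which is not shown. This stands for the final analysis. A reader might infer that the protocol has chosen an unadjusted final test; the text does not say so. It does not stand for the futility rules, which are written on raw mortality.

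Second, nothing is broken. An unadjusted comparison is valid under randomisation, its error rate already allows for chance imbalance, and the design meets its stated power. This stands in full.

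Third, a reader might infer from the blocking that leaving hospital out of the analysis loses power or distorts the test. The simulations show neither. A reader might also take the baseline variables to be strong predictors. Sections 5.1 and 5.2 only list what is recorded, so the gain can be given only as a range over assumed strength.

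Fourth, adjustment raises practical questions. Look 1 has about 250/24 ≈ 10 patients per hospital. A simulation of that look with one indicator per hospital and no pooling (2,000 trials, assumed unequal hospital sizes and covariate effect) left about 5 of 24 hospitals uninformative. The treatment log-odds ratio averaged −0.76 against a true −0.68, although type I error was not inflated. This stands as a condition on the fix.

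**Conclusion.** The point holds as a recommended improvement, not as an error. As described, the mortality comparison uses neither baseline covariates nor the hospital blocking, and the final test is unnamed.

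Adjustment for patient-level covariates would add about 0.6 to 5.6 points of power for R² between 0.02 and 0.20. An R² slightly above 0.05 would bring power to 90%, the level Section 6 itself uses when it checks the futility boundary. At R² = 0.10 adjustment would remove imbalance noise of about ±1.9 points at 750 patients and ±2.3 at 500. The latter is about the size of the 2-point futility threshold, though it is only a tenth of the total sampling variance.

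All of these sizes rest on the assumed R². Hospital contributes under 0.5 points, and the reason to include it is consistency with the randomisation. The calculations do not support calling the trial underpowered or its test invalid.

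**What to change.** In Section 6, before unblinded data are seen:

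- **Primary analysis.** Name it: logistic regression of the primary endpoint on treatment and a short fixed list of covariates, reported as a standardised absolute risk difference. Age, baseline PaO₂/FiO₂, vasopressor use and admission type would serve, taking age to be part of the demographic data. State that the values used precede any protocol ventilator change, and how missing values are handled.
- **Hospital.** Account for it by a method that is stable at about 10 patients per hospital, such as a random intercept or pooling of small hospitals by a stated rule.
- **Efficacy looks.** Compare the adjusted z with 2.0·√(3/i) at each look.
- **Futility looks.** State whether the two rules use the adjusted risk difference or stay on raw rates. Otherwise the two sets of boundaries could act on different estimates.
- **Supportive analysis.** Report the unadjusted difference.

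The cost is protocol or analysis-plan wording and a little programming. The listed variables are among the baseline data already planned, and no patient's treatment changes. The downside is slightly more complexity and reliance on complete baseline data.

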3.7 Minorities/Women

Gender and racial patient subsets were considered by the NHLBI in selecting the Network Centers. The demographic profiles of the Centers selected for the Network show that the aggregate ALI/ARDS patient population contains representative proportions of minorities (25%) and

women (39%). (Values from 6702 patients with ALI/ARDS in the ARDSnet 01 Screening Logs from March, 1996 - February, 1999). Recruitment of minorities and women will be monitored by the Network Coordinating Center. If necessary, additional recruitment efforts will be made at specific centers to ensure that the aggregate patient sample contains appropriate gender and minority subsets.

Randomization will result in approximately equal numbers of patients assigned to the treatment arms within each population subset. It will be possible to make statistical comparisons within these subsets; however, any inferences derived from these analyses will be of low power because of the relatively small number of patients within the subsets. The primary value of such analyses would be for generating additional hypotheses, which is appropriate given the current lack of evidence of gender or race-related interactions with the treatment interventions in the proposed study.

4 Study Procedures

4.1 Ventilator Procedures

4.1.1 Volume Cycled Ventilation

1. Ventilator mode: Volume Cycled Assist Control (all patients)
2. Tidal Volume, Ventilator Rate Setting, and Arterial pH Management.

- (a) Initial Ventilator Tidal Volume and Rate Setting.

Tidal Volume

(In the following procedures, the term “tidal volume” refers to inspired volumes, corrected for volume lost due to gas compression and ventilator conduit expansion.)

Predicted body weights (PBW) will be calculated for all patients([39]):

$$\text{Males: PBW (kg)} = 50 + 2.3 [\text{height (inches)} - 60]$$

$$\text{Females: PBW (kg)} = 45.5 + 2.3 [\text{height (inches)} - 60]$$

Initial tidal volumes in both treatment groups will be 8 ml/kg PBW. This will be reduced by 1ml/kg PBW at intervals of < 2 hours until tidal volume = 6 ml/kg PBW.

Ventilator Rate Setting

Both groups: initial ventilator rate setting will be adjusted to match minute ventilation prior to enrollment, if possible. Maximum rate setting will be 35/min.

(b) **Adjustments to Ventilator Tidal Volume and Rate.**

Goals: Ventilator rate and tidal volume will be adjusted to achieve goals of arterial pH and end-inspiratory plateau pressure, respectively.

Arterial pH Goals

- Goal for all patients: $7.30 \leq \text{pH} \leq 7.45$.
- Arterial pH will be measured when clinically indicated.
- Management of alkalemia and acidemia:
 - i. Alkalemia ($\text{pH} > 7.45$): Decrease ventilator rate, if possible.
 - ii. Mild acidemia ($7.15 \leq \text{pH} < 7.30$):
 - Increase ventilator rate up to maximum of 35 or until $\text{pH} > 7.30$ or $\text{PaCO}_2 < 25$ mm Hg.
 - If ventilator rate = 35 or $\text{PaCO}_2 < 25$, then bicarbonate infusion may be given.
 - iii. Severe acidemia ($\text{pH} < 7.15$):
 - Increase ventilator rate to 35.
 - If ventilator rate = 35 and $\text{pH} < 7.15$ and bicarbonate has been considered or infused, then tidal volume may be increased by 1 ml/kg until $\text{pH} \geq 7.15$ (under these conditions, the plateau pressure targets described below may be exceeded).

Plateau Pressure Goals

- Goal for all patients: ≤ 30 cmH₂O.

Plateau pressures will be measured at a minimum frequency of q4 hours. Plateau pressures will also be measured and recorded 1-5 minutes after each change in PEEP or tidal volume. For each measurement, patients will be relaxed, not coughing or moving. The pressure corresponding to the first plateau that occurs after initiating a 0.5 second pause will be recorded. If plateau pressures cannot be measured because of air leaks, then peak inspiratory pressure will be substituted.

Tidal volumes will be reduced by 1 ml/kg PBW q2-3 hours if necessary to maintain plateau pressures ≤ 30 cm H₂O. (If arterial pH < 7.15 , tidal volume need not be reduced; see section 2(b)iii, management of severe acidemia).

The minimum tidal volume in both groups will be 4 ml/kg PBW.

Changes in the tidal volume, if indicated above, will be made within five minutes.

Tidal volume < 6 ml/kg will be increased if plateau pressure \ll target:

- i. If tidal volume < 6 ml/kg PBW and plateau pressure < 25 cmH₂O, then tidal volume will be increased by 1 ml/kg PBW until plateau pressure > 25 cmH₂O or tidal volume = 6 ml/kg PBW.
- ii. If tidal volume < 8 ml/kg PBW AND P_{plat} < 30 cmH₂O AND airway pressure remains below the PEEP level during inspiration or the ventilator delivers frequent (>3 /minute) double breaths because airway pressure or flow-by falls below trigger threshold at the end of inspiration, then tidal volume will be increased by 1 ml/kg PBW. If these phenomena persist at tidal volume 8 ml/kg PBW or with P_{plat} > 30 cm H₂O, additional sedation or neuromuscular blockade should be considered.

3. Inspiratory flow and I:E ratio.

Inspiratory flow rate will be adjusted to achieve I:E = 1:1 - 1:3. Peak flow and inspiratory waveforms will not be standardized.

4. Oxygenation.

In both treatment groups, target ranges for oxygenation will be:

$$55 \text{ mmHg} \leq \text{PaO}_2 \leq 80 \text{ mmHg}$$

or

$$88\% \leq \text{SpO}_2 \leq 95\%$$

When both PaO₂ and SpO₂ are available simultaneously, the PaO₂ will take precedence.

Oxygenation will be maintained in the target ranges using the following PEEP/FiO₂ combinations:

Lo-PEEP/Hi-FiO₂ Treatment Group FiO₂

FiO ₂	.30	.40	.40	.50	.50	.60	.70	.70	.70	.80	.90	.90	.90	1.0
PEEP	5	5	8	8	10	10	10	12	14	14	14	16	18	18-24

Hi-PEEP/Lo-FiO₂ Study Group FiO₂

FiO ₂	.30	.30	.30	.30	.30	.40	.40	.50	.50	.50-.80	.80	.90	1.0	1.0
PEEP	5	8	10	12	14	14	16	16	18	20	22	22	22	24

(Levels of PEEP in these FiO₂/PEEP scales represent levels set on the ventilator, not levels of total-PEEP, auto-PEEP, or intrinsic-PEEP.)

- (a) Minimum initial FiO₂/PEEP setting in the Higher ELV/Lower FiO₂ group will be .30/12.
- (b) FiO₂/PEEP setting may not be decreased from its initial level (compatible with the oxygenation goals) in the Higher ELV/Lower FiO₂ group for at least 12 hours after initial protocol ventilator adjustments. Arterial oxygenation may exceed goals during this initial 12hour interval.
- (c) **Recruitment maneuvers (RM)** will be performed in the Higher ELV/Lower FiO₂ group within one hour of the initial FiO₂/PEEP adjustments, once daily (between 0600-1000), after disconnections of the endotracheal tube from the ventilator circuit, and after coughing or agitation that causes (within 5 minutes) a sustained (≥ 10 minutes) decrease in SpO₂ of $\geq 5\%$ or in PaO₂ of ≥ 15 mmHg. No more than 4 recruitment maneuvers will be performed in any 24-hour interval. Each recruitment maneuver will be documented.

RMs will be performed as follows if systolic blood pressure = 100-200 mmHg, heart rate = 70-140, and there were < 4 RMs in the preceding 24 hours:

- (a) If FiO₂ < .90, FiO₂ will be raised to 0.90 for 5 minutes.
- (b) Ventilation mode will be changed to CPAP = most recent PEEP level.

- (c) CPAP will be increased over 10 seconds to 40 cmH₂O (to 45 cmH₂O if measured wt. \geq 150% PBW).
- (d) CPAP will be maintained at 40 (or 45) cmH₂O for 45 seconds.
- (e) The RM will be terminated immediately and CPAP returned to the most recent PEEP level if any of the following signs of distress occur:
 - Systolic blood pressure decreases to 90 mmHg or by > 30 mmHg.
 - Heart rate increases to > 140 /min or by > 20 /min.
 - SpO₂ decreases by 5% and is $< 90\%$
- (f) After 45 Seconds at CPAP = 40 (or 45) cmH₂O, CPAP will be decreased over 5 seconds to the pre-RM level.
- (g) Most recent ventilation settings (Mode, tidal volume, PEEP/FiO₂, etc) will be resumed upon completion or early termination of RM.
- (h) If 2 RMs require early termination within a single 24 hour interval, no additional RMs will be attempted for at least 12 hours.

Arterial oxygenation will be assessed by either SpO₂ or PaO₂ at least every 4 hours. When SpO₂ is used to assess arterial oxygenation, the following measures will be taken if possible to improve accuracy: the SpO₂ sensor will be checked to ensure optimal position, cleanliness, and consistent readings with satisfactory waveforms; no position changes or endobronchial suctioning for at least 10 minutes; no invasive procedures or ventilator changes for at least 30 minutes. SpO₂ will be observed for a minimum of 1 minute, and a representative value will be recorded on the appropriate source-document flowsheet.

If arterial oxygenation is not within the target range, then either FiO₂ or PEEP will be adjusted within 30 minutes. Following these adjustments, oxygenation will be reassessed within 15 minutes and subsequent adjustments made if necessary.

If a patient's PEEP/FiO₂ is not compatible with the PEEP/FiO₂ scale (e.g. immediately after randomization or after urgent changes in FiO₂ or PEEP in response to desaturations, hypotension, etc.), either PEEP or FiO₂ (or both) will be

adjusted at intervals of 5-15 minutes (according to Appendix D) until the PEEP/FiO₂ is compatible with the scale.

In both treatment groups, if PaO₂ < 55 mmHg or SpO₂ < 88% and tidal volume = 4 ml/kg PBW (or the minimum tidal volume necessary for pH control, section 4b above) and plateau pressure ≥ 30 cmH₂O, then FiO₂ will be raised until PaO₂ = 55-80 mmHg or SpO₂ = 88-95% or FiO₂ = 1.0. If PaO₂ < 55 mmHg or SpO₂ < 88% and FiO₂ = 1.0, PEEP will be raised by 2 cmH₂O increments to 24 cmH₂O. In these circumstances, plateau pressure may exceed 30 cmH₂O.

Brief periods (5 minutes) of SpO₂ < 88% or > 95% may be tolerated without making changes in PEEP or FiO₂.

FiO₂ = 1.0 may be used for brief intervals (10 minutes) of transient desaturation or to prevent desaturation during treatments such as tracheo-bronchial suctioning or position changes.

If FiO₂ = 1.0 and PEEP = 24 cmH₂O and PaO₂ < 55 or SpO₂ < 88%, then a PEEP increase trial may be performed as follows:

- (a) Increase PEEP by 2-5 cmH₂O increments to a maximum of 34 cmH₂O or until PaO₂ = 55-80 mmHg or SpO₂ = 88-95%.
- (b) If the PEEP increase trial does not lead to an increase in PaO₂ of ≥ 5 mmHg within 4 hours, PEEP will be set = 24 cmH₂O.

In both study groups, in-line suction catheters will be encouraged to avoid unnecessary disconnections of the ventilator circuit from the endotracheal tube.

In both study groups, endotracheal suctioning will be conducted after changing the ventilator mode to Pressure Support = 15 cmH₂O.

5. Simultaneous changes

Changes in more than one ventilator setting driven by measurements of PO₂, pH, and plateau pressure may be performed simultaneously, if necessary. Arterial blood gases will be obtained after all ventilator changes as clinically indicated.

